3. STUDY PROCEDURES AND ASSESSMENTS

3.1. Safety Assessments

- Physical Examination Including Vital Sign Results
- Pregnancy Tests

3.2. Efficacy Assessments

- The number of facial BCCs removed by surgery (per Investigator determination) and histologically verified as BCC; from Baseline to Month 12
- The number of facial BCCs removed by surgery (per Investigator determination) and histologically verified as BCC; from Baseline to Month 6
- The number of facial BCCs removed by surgery (per Investigator determination) from Baseline to Month 12
- The number of facial BCCs removed by surgery (per Investigator determination) from Baseline to Month 6
- Change from Baseline to Month 12 in the total number of facial lesions suspicious for BCC
- Count of facial lesions suspicious for BCC over time
- aBCCdex change in lesion score from Baseline to Month 12

3.3. Exploratory Assessments Patient Reported Outcomes

Exploratory assessments will comprise the following Patient Reported Outcomes (PROs) of Quality of Life:

- Advanced Basal Cell Carcinoma index (aBCCdex)
- Dermatology Life Quality Index (DLQI)
- EuroQol Group 5-level EQ-5D (EQ-5D-5L)

3.4. Baseline Variables

3.4.1. Study drug, study treatment and baseline definitions

In this study, either 'study drug', 'study treatment' or 'Investigational product (IP)' refer to Patidegib Topical Gel, 2%.

Start and end dates of study treatment:

The date/time of first dose of study treatment is the earliest date/time of non-zero dosing of the study drug.

The date/time of last dose of study treatment is the latest date/time of non-zero dosing of the study drug.

Definition of baseline:

In this study, baseline value will refer to the last assessment prior to the first dose.

3.4.2. Baseline characteristics

- Inclusion and exclusion criteria
- Demographic data
- Medical history
- Prior and concomitant medication

4. ANALYSIS POPULATIONS

Only patients who signed the Informed Consent Form (ICF) will be included in the analysis sets described below.

4.1. Safety Population

The safety analysis set will include all patients who had at least one application of study treatment. The primary population for analysis of safety and efficacy will be the safety population.

Subgroup analysis will be done for subjects with history of oral or topical HHI in past 6 months – Yes/No. This will be determined based on the group they were randomized in the parent study (i.e. either 201 or 301) and the previous and concomitant medication pages.

The following efficacy assessments will be analyzed for the forementioned subgroups:

- The number of facial BCCs removed by surgery (per Investigator determination) and histologically verified as BCC; from Baseline to Month 12
- The number of facial BCCs removed by surgery (per Investigator determination) from Baseline to Month 12
- Change from Baseline to Month 12 in the total number of facial lesions suspicious for BCC

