4 INTRODUCTION

PellePharm, Inc. (PellePharm) is developing a topical formulation of patidegib for the mitigation of the disease burden of persistently developing basal cell carcinomas (BCCs) in patients with Gorlin syndrome and a high frequency of BCCs (HF-BCC). There are currently no approved therapies for Gorlin syndrome or HF-BCC. The continuous development of BCCs, especially on the face, can lead to seriously disfiguring scars and functional impairment, resulting in a significant decrease in quality of life. It is hoped that, by decreasing the number of surgeries that these patients require, their quality of life will be greatly improved.

Three clinical interventional studies of Patidegib Topical Gel have been completed by PellePharm, Inc. while a fourth study is ongoing. The safety of the oral formulation was characterized before the topical was advanced to the clinic (Patidegib IB).

the limited data from the three studies, Patidegib Topical Gel was found to be safe and tolerable. Patidegib Topical Gel is currently being evaluated in Study Pelle-926-301 – a Phase 3 double blind randomized vehicle controlled study in patients with Gorlin syndrome.

This current study is an open label extension study offered to patients with Gorlin syndrome who participated in studies 926-201 or 926-301. The objective of this study is to evaluate safety and efficacy on an ongoing basis.

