7.1.2 Subject Exclusion Criteria

Subjects meeting any of the following criteria will be excluded from the study.

1. The subject has used topical treatment to the face or systemic therapies that might interfere with the evaluation of the study IP. Among these are use of the following:

- 2. The subject has a known hypersensitivity to any of the ingredients in the study IP formulation.
- 3. The subject is unable or unwilling to make a good faith effort to return to the study site for all study visits and tests.
- 4. The subject has current, recent (within five half lives of the experimental drug or if half life not known, within the past 6 months prior to the Screening Visit), or planned participation in an experimental drug study (excluding Study 926-301) while enrolled in this study.
- 5. The subject is a WOCBP who is unwilling or unable to comply with pregnancy prevention measures.
- The subject is pregnant or breastfeeding.
- 7. The subject has any condition or situation which, in the Investigator's opinion, may put the subject at significant risk, could confound the study results, or could interfere significantly with the subject's participation in the study. This may include a history of other skin conditions (e.g., severe facial eczema) or diseases, metabolic dysfunction, physical examination (PE) findings, or clinical laboratory findings giving reasonable suspicion of a disease or condition that contraindicates use of an investigational drug or that might affect interpretation of the results of the study or render the subject at high risk from treatment complications.

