12 STATISTICS

12.1 Analysis Population

The primary population for analysis of safety and efficacy will be the Safety population. This population will comprise all patients who had at least one application of study treatment. Subgroup analysis will be done for subjects with history of oral or topical HHI in past 6 months – Yes/No.

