6.3.1.3. Prior and concomitant medications/therapies

Prior and concomitant medications/therapies will be captured separately for BCC (facial) and other indications.

All medications ongoing in the 12 months prior to Baseline or ongoing at any time during the study will be recorded in the eCRF. The start date for all medications that were started during the study period must be reported. Likewise, the end date for all medications that were discontinued during the study period must be captured.

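### SAP 4.1 defines a subgroup by hedgehog inhibitor (HHI) use in the past 6 months but names sources that do not reliably date the last exposure, so patients last treated longer ago can be classed 'Yes'

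*SAP*

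**What the plan says.** Protocol 12.1 defines the subgroup by "history of oral or topical HHI in past 6 months", and SAP 4.1 repeats it: "Subgroup analysis will be done for subjects with history of oral or topical HHI in past 6 months – Yes/No". SAP 4.1 then explains how patients are assigned: "This will be determined based on the group they were randomized in the parent study (i.e. either 201 or 301"). The same sentence goes on to name a second source: "and the previous and concomitant medication pages". The split applies to three endpoints: histologically verified facial BCC removals to Month 12, all facial BCC removals to Month 12, and change to Month 12 in facial lesions suspicious for BCC. SAP 2 states that the SAP overrides the protocol's statistical plans, so SAP 4.1 is the operative rule.

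On the medication pages, SAP 6.3.1.3 says: "All medications ongoing in the 12 months prior to Baseline or ongoing at any time during the study will be recorded in the eCRF". On stop dates it adds that "the end date for all medications that were discontinued during the study period must be captured". Under SAP 5.3.2.2, a medication date that is missing completely is set to the start of study treatment.

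On timing, Protocol 4 reports: "Three clinical interventional studies of Patidegib Topical Gel have been completed by PellePharm, Inc. while a fourth study is ongoing". It names Study 301 as the study still running, which places Study 201 among the completed ones.

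**The concern.** The subgroup is defined by time, but its first named source is an allocation. The arm shows whether a patient was assigned patidegib or vehicle. It does not show when the last application took place. For a patient who moves straight from Study 301 into this study, the two come to the same thing. For a Study 201 patient they may not.

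Protocol 6 says that former vehicle patients now receive active gel, so the population mixes patients who continue, start and possibly restart treatment. The SAP plans no summary by parent study or parent arm, which leaves this as its only split by prior exposure. With descriptive summaries and no model, a misassigned patient enters the reported table directly, under a label that is untrue for that patient. If such patients resemble the 'No' group, the Yes-No contrast shrinks. Two programmers following SAP 4.1 could also build different subgroups.

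**Working it through.** The plan gives no figure for this subgroup to reproduce. The check compares the definition with the sources named for it, then illustrates what misassignment could do.

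**1. What each source can date**

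- *Randomized arm (SAP 4.1):* no date.
- *Medication pages (SAP 6.3.1.3):* the look-back is 12 months before Baseline, longer than the 6-month window. Being listed therefore does not establish use within 6 months. Stop dates are expressly required only for drugs stopped during the study, so an HHI stopped before entry may have none. Nothing says that parent-study gel is recorded on these pages.
- *Missing dates (SAP 5.3.2.2):* replacing a completely missing date by the start of treatment could itself create a recent exposure that did not occur.
- *Not stated anywhere:* the date from which 6 months is counted, which source prevails if they differ, and whether the last parent-study application date is used.

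**2. Whether gaps over 6 months are plausible**

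- *Study 201:* the Investigator Brochure cited for its safety results is dated 25 March 2019 (Protocol 6.2 and 16). The protocol on which the SAP is based is Version 2 of 30 January 2020 (SAP 2).
 - 25 March 2019 to 30 January 2020 = 311 days.
 - With the SAP 5.2.4 conversion, 311 / 30.4375 = 10.2 months.
 - The window is 6 x 30.4375 = 182.6 days.
 - If Study 201 dosing had ended by the Brochure date, which is an assumption, no Study 201 patient entering on or after the Version 2 date would have parent-study exposure within 6 months. The synopsis keeps enrollment open until about when the last Study 301 patient finishes, so later entrants would have longer gaps.
- *Study 301:* Protocol 8.1 allows Screening on the day of the End of Treatment visit and requires Baseline within 30 days of Screening. It sets no maximum gap between End of Treatment and Screening, and rescreening is allowed.

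**3. Illustration of dilution**

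Let f be the share of the 'Yes' group with no HHI in the past 6 months, and suppose those patients behave like 'No'. Then

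observed difference = (1 - f) x true difference.

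Assume 200 enrolled (the plan's approximate maximum), the same active-arm share a in both parent studies, every active-arm patient classed 'Yes', every Study 201 patient beyond 6 months, every Study 301 patient within it, and no other HHI use. Then f = (a x n201) / (a x 200) = n201 / 200, so a cancels.

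| Study 201 patients (assumed) | f | Share of difference kept |
|---|---|---|
| 5 | 2.5% | 97.5% |
| 10 | 5% | 95% |
| 30 | 15% | 85% |
| 50 | 25% | 75% |

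The documents give neither the number of Study 201 entrants nor the allocation in either parent study. The table shows how the result depends on them and is not an estimate. Under a dated rule f = 0.

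**The case against.** The strongest defence is that the 6-month definition still governs and the next sentence only names data sources. The arm is needed because Study 301 is double-blind and vehicle-controlled, so participation alone does not show whether the gel contained an HHI. On that reading the arm does not replace the time window, and the medication pages cover other HHIs with a look-back longer than 6 months. This stands in part. A reader might infer that the SAP classes every active-arm Study 201 patient as recently exposed, or that the medication pages can never turn an arm-based 'Yes' into 'No'. The SAP says neither; it leaves the combination open. But on the defence's own reading, the named sources still lack the date needed to apply the definition.

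A reader might also take the eligibility rule as proof that Study 201 patients are beyond 6 months. Exclusion 4 in Protocol 7.1.2 bars recent or planned "participation in an experimental drug study (excluding Study 926-301) while enrolled in this study" and exempts only Study 301. Its window, however, is five half-lives, with 6 months only as the fallback when the half-life is unknown, and the documents give no half-life for patidegib. The treatment list under exclusion 1 is absent from the public text, so any HHI washout there cannot be checked.

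Three further objections hold. The 311 days run between two document dates, neither of which is a last-dose or entry date. Dilution toward no difference assumes that washed-out patients behave like 'No', and the documents give no duration of effect after stopping. The documents do not call this a carry-over comparison; it is a descriptive split without testing. For Study 301, the visit rules point to close succession for most patients, so a long gap there is possible rather than expected.

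**Conclusion.** The point holds as a defect in the derivation rule: a time-defined subgroup is assigned from sources that do not reliably date the last exposure. Active-arm Study 201 patients are those most likely to receive a false 'past 6 months' label, and a late-entering Study 301 patient could receive one too. That this can happen follows from the text. That it will happen, and to how many, does not.

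A reader might conclude that the subgroup contrast is materially diluted. The documents do not support that, because the 2.5% to 25% range rests entirely on assumed numbers of Study 201 entrants and on the other assumptions listed with it. The consequence is confined to three descriptive efficacy summaries. The primary safety objective is unaffected, and no test or power statement is involved. The rule should still be corrected, because the present wording allows more than one subgroup and the correction is small.

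**What to change.** Replace the assignment sentence in SAP 4.1 with a rule based on dates. A patient is 'Yes' if the last application of active parent-study gel in Study 201 or 301, or the last dose of any other oral or topical HHI, falls within 6 months (183 days) before the first application in this study; otherwise 'No'. Take the arm and the last-application date from the parent database. List days since last HHI dose for each patient. A separate line for patidegib exposure more than 6 months earlier is optional.

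For HHIs other than parent-study gel, the rule needs a stop date even when use ended before entry. Missing dates for these entries should be queried, so that the replacement rule in SAP 5.3.2.2 does not decide the flag.

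The cost is SAP wording, one extra variable merged from databases the sponsor must open anyway to obtain the arm, and date queries for any other HHI entries. The 'Yes' group may become slightly smaller. No visit, assessment or treatment changes.

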4.2. Other Population

4.2.1. Per-protocol Population

The Per-Protocol set (PPS) will include all subjects in the Safety population who have no major Protocol Deviations (PDs). The final criteria for the PPS will be determined when all data on PDs are available through a Data Review Meeting (DRM). Data for all patients will be assessed to determine if patients meet the criteria for inclusion in each analysis population prior to releasing the database (i.e. Database Lock) and classifications will be documented per TFS's (or Sponsor's) standard operating procedures. Patients who meet any of the following criteria may be excluded from the PP analysis set:

- Patient with any major protocol violations in regards to inclusion/exclusion criteria
- Patient not completing 12 months of treatment with 80% 120% treatment compliance (see Section 6.3.3)
- Patient taking any prohibited concomitant medications.

All PDs will be reported to PellePharm and recorded throughout the study. A tabulation of PDs will be included in the final study report.

4.2.2. PK Population

Not Applicable.

5. GENERAL METHODOLOGY AND CONVENTIONS

5.1. Sample size determination

As stated in the CSP, this study is not powered for statistical significance. Eligible subjects (completers) from PellePharm Studies 926-201 and 926-301 will be enrolled into this study up to a maximum of about 200 participants.

5.2. General Methods

Endpoints will be summarized based on either the Safety or the PP analysis sets.

5.2.1. Presentation of continuous and qualitative variables

Continuous variables will be summarized using descriptive statistics i.e., number of nonmissing values and number of missing values [i.e., n (missing)], mean, median, standard deviation (SD), minimum, maximum and first and third quartile (Q1 and Q3).

Qualitative variables will be summarized by frequency counts and percentages based on number of available observations. Missing data will not be summarized as a separate category.

In case the analysis refers only to certain visits, percentages will be based on the number of patients still present in the study at that visit, unless otherwise specified.

5.2.2. Definition of study day

Start day of study treatment is the day of the first IP application of study treatment.

The study day for assessments occurring on or after the start of study treatment will be calculated as:

Study day = Date of the assessment/event - start of study treatment + 1.

The study day for assessments occurring prior to the first IP application of study treatment will be negative and calculated as:

Study day = Date of the assessment/event - start of study treatment.

The study day will be displayed in all relevant data listings.

5.2.3. Definition of on-treatment period

Safety endpoints will be summarized based on the on-treatment period unless otherwise specified.

On-treatment period is defined as the time from the first IP application of study treatment to last IP application of study treatment + 30 days.

Safety data collected outside the on-treatment period as well as data from unscheduled visits will be listed and flagged in listings but not summarized.

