5.2.5. Unscheduled visits

Subjects may return to the site for unscheduled visits in the event of an AE, SAE or as deemed necessary by the Investigator. The same procedures as per any other post-Baseline Visits may be conducted. Data collected will be reported in the 'Unscheduled Visit' eCRF page.

Data from unscheduled visits will be summarized by assigning to closest visit within a 6-week window. If two unscheduled visits occur in a row the last one will be assigned (Last Observation Carried Forward approach).

All unscheduled visits info will be listed, flagging those that have been assigned to a prescheduled visit.

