6. ANALYSES AND SUMMARIES

6.1. Primary Endpoints

6.1.1. Safety and Tolerability.

Safety and tolerability are the primary objectives of this study and will be evaluated by reviewing adverse events (see Section 6.4.2), treatment discontinuations and dermal safety and tolerability (see Section 6.4.1).

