6.4.1. Dermal Safety and Tolerability

Dermal safety and tolerability will be evaluated through assessment of selected local signs and symptoms (pain/burning, pruritus, erythema, edema, and crusting) on the face. Any local skin reaction that requires use of a concomitant therapy or causes interruption or discontinuation of the IP should be reported as a dermal safety event. These events will be assessed for severity, relative to the skin reactions scale.

Shift tables of the frequency of dermal safety and tolerability assessments including pain/burning, pruritus, erythema, edema, and crusting will be summarized using counts and percentages by visit compared to baseline.

A listing of all dermal safety and tolerability assessments will be also provided.

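### SAP 5.2.3 and 5.2.5 give opposite rules for unscheduled-visit data, so the by-visit dermal tables in the primary safety evaluation depend on which rule is followed

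*SAP*

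**What the plan says.** SAP 5.2.3, which defines the on-treatment period for safety endpoints, ends: "Safety data collected outside the on-treatment period as well as data from unscheduled visits will be listed and flagged in listings but not summarized".

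SAP 5.2.5 opens with visits prompted by an AE, an SAE or the investigator's judgement, and adds: "The same procedures as per any other post-Baseline Visits may be conducted". It then says: "Data from unscheduled visits will be summarized by assigning to closest visit within a 6-week window". Where two unscheduled visits follow one another it uses the later one, and labels this Last Observation Carried Forward. It closes: "All unscheduled visits info will be listed, flagging those that have been assigned to a prescheduled visit".

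SAP 6.1.1 names dermal safety and tolerability as one of three components of the primary evaluation. Under SAP 6.4.1 the shift tables for the five dermal items "will be summarized using counts and percentages by visit compared to baseline", and every dermal assessment is listed. No table of the worst post-baseline score is planned.

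SAP 6.4.4 bases the vital-sign summaries on every assessment made in the on-treatment period. SAP 6.2.2 summarizes the efficacy assessments by visit.

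**The concern.** The two sections answer the same question in opposite ways. Even the flags differ: 5.2.3 marks data left out of the summaries, while 5.2.5 marks visits that have been brought into them. Two programmers following this SAP could produce different dermal shift tables for part of the primary evaluation. In an open-label study with no hypothesis test, those descriptive tables are the result. A rule settled after the scores are known would be open to question.

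A second issue follows. Unscheduled visits may be prompted by a skin reaction, so the disputed data can include scores taken when the reaction was at its height. If those scores are dropped, or replaced by a later and milder one, the dermal tables can understate the worst reaction.

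**Working it through.** The plan gives no figure to reproduce here. The check compares the texts and then does simple arithmetic.

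**Is there a tie-breaker?** The exception clause in 5.2.3 belongs to its sentence on summarizing safety endpoints over the on-treatment period, not to its sentence on unscheduled visits. SAP section 2 places the SAP above the protocol but does not rank its own sections. For vital signs, 6.4.4 points towards inclusion, which also conflicts with 5.2.3.

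**Window.** Inputs: 1 month = 30.4375 days (SAP 5.2.4); quarterly visits (Protocol 8.1), assumed to fall on target.

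- Interval between visits: 3 × 30.4375 = 91.3 days.
- Six weeks either side: 91.3 − 2 × 42 = 7.3 days unassigned (8.0%). The Month 3 window opens at 91.3 − 42 = 49.3 days.
- Six weeks in total (21 days either side): 91.3 − 42 = 49.3 days unassigned (54.0%). The Month 3 window opens at 91.3 − 21 = 70.3 days.
- A score at 60 days lies 31.3 days from Month 3, so it is assigned only under the wider reading.
- Baseline is pre-dose (SAP 3.4.1). For quarterly patients, even the wider reading therefore gives an unscheduled score in the first 49 days no post-baseline cell.
- Women of childbearing potential attend monthly, and the nearest visit may be one at which Protocol Table 1 schedules no dermal assessment.

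**One hypothetical patient (assumed scores).** Erythema is 0 at Baseline and 0 at Month 3, then 3 and 1 at unscheduled visits 100 and 107 days after first application. These lie 8.7 and 15.7 days from Month 3, inside both windows.

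| Reading | Month 3 shift |
|---|---|
| 5.2.3 | 0 to 0 |
| 5.2.5, unscheduled value replaces scheduled | 0 to 1 |
| 5.2.5, scheduled value stands | 0 to 0 |

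The score of 3 is in no dermal table under any of the three. With a single unscheduled visit scored 3 and replacement allowed, 5.2.5 would show it. So 5.2.5 can capture the peak but does not guarantee it.

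**Which items are exposed?** In Protocol Table 2, erythema, edema and crusting have no look-back, so a later visit cannot recover their peak. Pain/burning and pruritus are scored at their greatest intensity since the previous visit. If that means the previous scheduled visit, the Month 6 score should recover a peak at 100 days. If an unscheduled visit at 107 days resets the recall, it would not.

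**Size per patient.** SAP 5.2.1 uses patients still present at the visit as denominator, so one patient moves a cell by 100/N points: 0.5 at N = 200 (the stated approximate maximum), 1.0 at N = 100 and 2.0 at N = 50 (both assumed). At N = 200, an assumed 1 to 10 affected patients gives 0.5 to 5.0 points.

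**The case against.** **The rules might be split by data type.** The disputed sentence in 5.2.3 begins with safety data, so it could be the safety rule and 5.2.5 the rule for everything else. That 5.2.5 mentions AE visits does not exclude this, because an AE visit can also yield lesion counts. The reading is possible but nowhere stated, and 6.4.4 does not fit it. The ambiguity stands.

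**The plan promises no peak.** Protocol 12.7.1 and SAP 6.4.1 commit only to by-visit summaries, and a by-visit table shows status. This is fair: the missing worst-score table is a gap, not a contradiction. Dermal scoring at unscheduled visits is also optional, so a worst score partly reflects how often a patient attended.

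**The consequences are limited.** This also stands. Analyses are descriptive and all dermal scores are listed. SAP 6.4.1 adds: "Any local skin reaction that requires use of a concomitant therapy or causes interruption or discontinuation of the IP should be reported". Reactions reported as AEs reach the TEAE tables by maximum severity, though on the AE severity scale rather than the dermal scale.

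**Inferences the documents do not support.** A reader might infer that severe reactions vanish from the report; the listings and AE reporting say otherwise. A reader might also infer that only dermal and vital-sign summaries are touched. That holds only if the 5.2.3 clause is confined to safety data; otherwise the by-visit lesion counts are affected too. Nor do the documents establish that exactly three of the five dermal items are exposed, because Table 2 does not say whether an unscheduled visit resets recall.

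**Conclusion.** The contradiction is real and should be resolved before database lock. The by-visit dermal shift tables and vital-sign summaries depend on which section is followed, and the lesion counts may as well. Section 5.2.5 cannot be programmed without deciding what the window means and what happens when a scheduled value exists. Neither section guarantees that a peak dermal score from an unscheduled visit reaches a dermal table. This is clearest for erythema, edema and crusting, and conditional for pain/burning and pruritus.

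The 7.3-day and 49.3-day gaps assume quarterly visits on target. The patient's scores and the 1 to 10 affected patients are illustrative. The total size and direction of the effect cannot be derived, because the documents do not say how many unscheduled dermal scores to expect. No inferential conclusion is at risk.

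**What to change.** 1. In SAP 5.2.3, strike the clause on unscheduled visits, so that the sentence covers only data outside the on-treatment period and 5.2.5 is the single rule.
2. In SAP 5.2.5, for point-in-time assessments only (dermal scores, vital signs, current count of suspicious lesions):
   - give the window as a half-width in days around visits at which that assessment is scheduled;
   - let an unscheduled value fill a missing scheduled cell but never overwrite a scheduled value;
   - if several values qualify, name one pick. The last can stay, since these tables show status;
   - drop the Last Observation Carried Forward label. An observed in-window value is not an imputation, so this agrees with SAP 5.3.1.
3. State that lesions removed, and those histologically confirmed, are summed over the whole interval, including any recorded at unscheduled visits. Protocol 8.2 records removals as counts since the previous visit, so a fill-only rule applied to them could drop lesions from efficacy endpoints 1 to 4.
4. Add to SAP 6.4.1 a shift table from baseline to the worst post-baseline score for each of the five dermal items, using all on-treatment scheduled, unscheduled and early-termination assessments. It also captures early scores that have no by-visit cell.

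The cost is SAP wording and one extra table from data already collected. The downsides are a table to explain, dermal rates that may look less favourable, and a worst score that rises with attendance; a footnote should state the last point.
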